3. STUDY METHODS AND PROCEDURES

3.1. Study Treatment/Intervention

If the woman completes the consent form, they will be enrolled in the study and randomized into either the intervention or control group. When they are admitted to the postpartum unit after cesarean delivery, based on their randomization, the study coordinator at each site will schedule either 1) a Healing Touch (HT) practitioner for the intervention group OR 2) a non-HT practitioner who will collect data for the control group. The HT practitioners for this study will be registered nurses or HT practitioners who work in the Inova Health System and have received the minimum of Foundations of Healing Touch training. All study personnel entering patient care areas will abide by universal precautions, plus masks and face shields as required by the hospital system for infection control. For the intervention group, the HT practitioner will verify consent. Then they will ask the woman to complete baseline measurements of pain and anxiety. The practitioner will then administer the HT intervention consisting of a full body, pain management technique focusing on the surgical site, and wound sealing. HT techniques (Field Repatterning, Pain Syphon, Beak Fingers Lasering,) are techniques specific to management of pain and clearing of the energy field that have been used frequently by the nurses in their delivery of patient care. The HT intervention to be used in the proposed study has been developed by co-investigator, [name], Certified Healing Touch Practitioner and Instructor, to focus on the symptom management needs of the study participants (post-cesarean delivery) and should take no more than 15 minutes to complete. Levels of pain and anxiety will be reassessed post-intervention. Nurses providing the HT intervention will document the session and other outcomes as described below. There is a risk that the patient will not receive Healing Touch if: there is not a HT provider available or the patient is discharged prior to availability of the HT provider.

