3.2. Control Group

This study has a control group. For the control group: a member of the research team, who may or not be a HT practitioner, will verify consent. Then they will ask the woman to complete baseline measurements of pain and anxiety. The subject will then be encouraged to have a quiet time session equivalent to the length of a Healing Touch session, with the lights dimmed. After the quite time, the team member will again measure the subject's levels of pain and anxiety.

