The study Sub-Investigators at each site will follow the same procedure. Once a potential study subject has been enrolled in the study they will receive a coded study "ID" which will consists of numbers and letters. Any data collected during the study will be coded with this study ID. After being randomized into the intervention group or control group, and based on their scheduled delivery date, the study site coordinator will schedule the subject for either a session with a Healing Touch practitioner, or a session of quiet time (the control) with a member of the study team. The Demographic Form (Appendix D) and Data Collection Form (Appendix K) will be labeled with the patient identification sticker. This is to ensure that study personnel can use the sticker to accurately identify study subjects. After the data is collected from the session, the form will be put into a sealed envelope and given directly to the study site coordinator. The site coordinator will enter the data from the subject into the spreadsheet with the coded ID. This coded data will be shared securely with the study Primary Investigator, who will synthesize the data from the various study sites.

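### On the natural reading of the plan, the practitioner who gave Healing Touch also takes the post-session scores, while someone who gave no therapy takes them in the control arm

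*Combined protocol and SAP*

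**What the plan says.** **HT arm (section 3.1; the Abstract's Study Methodology is similar).** One person handles the start of the visit: "For the intervention group, the HT practitioner will verify consent", and "Then they will ask the woman to complete baseline measurements of pain and anxiety". The same practitioner gives the session. The next step names nobody: "Levels of pain and anxiety will be reassessed post-intervention". The section then adds: "Nurses providing the HT intervention will document the session and other outcomes as described below".

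**Control arm (section 3.2).** A team member asks for the baseline scores and encourages quiet time with dimmed lights. Then: "After the quite time, the team member will again measure" the woman's pain and anxiety.

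**Who runs the control session.** The sections differ. Section 3.1 (like the Abstract) describes "a non-HT practitioner who will collect data for the control group". Section 3.2 describes a team member "who may or not be a HT practitioner".

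**After recording (section 4.3.1).** Once the session data have been collected, "the form will be put into a sealed envelope and given directly to the study site coordinator", who enters them under a coded ID.

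**Outcomes and masking.** Pain and anxiety, before and after the session, are both primary (section 3.4.1). No masking of women, practitioners, collectors or analyst is described for this trial. The only mention of blinding, in section 1.3, concerns a cited Reiki study.

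**The concern.** Open allocation may be unavoidable with a hands-on therapy. What can be avoided is a difference between the arms in how the score is obtained. If the practitioner takes the post-session score, a woman in the HT arm rates her relief to the person who has just spent about 15 minutes treating her. A control woman rates hers to someone who gave no therapy. A wish to please the therapist, or prompting by the therapist, can lower recorded scores in the HT arm alone.

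Both primary outcomes are subjective ratings taken directly after the session. A shift of this kind would look the same as a treatment effect, on both outcomes at once. The sealed envelope does not prevent it, because the form is sealed after the score has been given. The privacy text in section 3.1 deals with visitors and the door sign, not with privacy from the practitioner.

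**Working it through.** **Step 1. Who takes the HT post-session scores?** There are three candidates.
- *The practitioner.* This person is in the room, has asked for the baseline scores and documents the session and outcomes. Section 3.1 also gives the control arm a person whose stated role is data collection, and gives the HT arm only a practitioner.
- *Another team member.* None is assigned anywhere.
- *The woman alone.* This is possible, since she completes the baseline ratings herself, but no section says that she does so afterwards or out of the practitioner's view.

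The first is the natural reading. It is an inference, not an explicit statement.

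**Step 2. Reproduce the plan's sample size (section 4.1).** Inputs: two-sided alpha 0.05, power 0.80, d = 0.5, equal allocation. For n per arm, the t-test has 2n − 2 degrees of freedom and noncentrality δ = d / √(2/n).
- n = 64: √(2/64) = 0.1768, δ = 0.5 / 0.1768 = 2.828, critical t (126 df) = 1.979, power = 0.8015.
- n = 63: power = 0.795.

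So 64 per arm, 128 in total, as stated.

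**Step 3. The same test with no true effect and a shift of b SD in the HT arm.** The shift b is an assumption. It is in SD units of the analysed variable, and δ = b / √(2/n). The 80-per-arm case is 160 women split equally.

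| b | δ, n = 64 | P(p < 0.05) | δ, n = 80 | P(p < 0.05) |
|---|---|---|---|---|
| 0 | 0 | 0.05 | 0 | 0.05 |
| 0.1 | 0.566 | 0.0868 | 0.632 | 0.0964 |
| 0.2 | 1.131 | 0.2023 | 1.265 | 0.2418 |
| 0.3 | 1.697 | 0.3915 | 1.897 | 0.4705 |

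The observed difference needed for significance is 1.979 × 0.1768 = 0.35 SD at 64 per arm and 1.975 × 0.1581 = 0.31 SD at 80. Recruiting 160 rather than 128 therefore makes a given shift more likely to reach significance.

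**Step 4. Points on the scale.** For pain, tabulated as 0-10, an assumed SD of 1.5 to 3 makes 0.2 SD equal to 0.2 × 1.5 = 0.3 up to 0.2 × 3 = 0.6 points.

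**Step 5. Can the analysis remove it?** The planned analysis (section 4.2) is a t-test. Suppose the HT post-session score is the true score minus b, and randomisation makes the baselines equal on average. The expected difference between arms is then b, whether the analysis uses post-session scores, change scores or baseline-adjusted scores. The shift arises after baseline, so nothing in the baseline carries information about it.

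**The case against.** The strongest reply is that the plan never says the practitioner takes the post-session scores. The sentence is passive, and the other outcomes that nurses document are not defined. Self-completion may already be intended: the woman completes her baseline ratings, inclusion requires that she can read English and complete assessments, and the data collection form (Appendix K) is not in the text available. This stands as a limit on certainty. It does not remove the point, because nothing in the text would prevent practitioner collection.

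Second, the arms may differ less than it seems. The control collector also knows the allocation, has encouraged the quiet time and, under section 3.2, may be an HT practitioner. This also stands in part. The difference that remains is that this person has given no therapy.

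Third, private completion has a cost. Each woman has one session (section 2.3), so a blank post-session score cannot be retaken. Section 7 relies on the principal investigator reviewing each woman's data. The form would still reach the coordinator and then the investigator by the existing route, but the sponsor should confirm that sealing it at the bedside fits its safety review.

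A reader might also infer that both outcomes are 0-10 scores. The documents do not support that: section 3.4.1 calls anxiety a Numeric Rating Scale without a range, then tabulates a Hospital Anxiety Scale scored 0-14. The argument needs only that both are subjective.

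**Conclusion.** The concern holds as an avoidable difference between the arms in who obtains two subjective primary outcomes. It rests on the natural reading of section 3.1 and on the absence of any described masking.

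The size is illustrative only. With no true effect, a between-arm shift of 0.1 to 0.3 SD would raise the false-positive rate per outcome from 5% to between 8.7% and 39% at 64 per arm, or between 9.6% and 47% at 80. These rates apply to a shift from any source. They do not measure the part due to the collector.

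Two stronger readings are tempting. One is that a positive result would be false: the documents give neither the size nor the direction of any bias, so the plan permits a spurious effect but does not show one. The other is that changing the collection method restores the 5% rate: it does not, because women know whether they received HT and expectation can still move their scores. The required sample size of 128 is unaffected.

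**What to change.** In sections 3.1 and 3.2 and in the data collection procedure, state one method for both arms:
- After the same scripted instruction, the woman writes her own pre- and post-session pain and anxiety scores on the form, out of view of the person running the session.
- She confirms that every item is filled in, and seals the form in the envelope already in use before handing it over.
- The control-arm sentence that has the team member measure again is replaced accordingly, and the practitioner's documentation is limited to the session itself.

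Reconcile the Abstract and section 3.1 with section 3.2 on whether an HT practitioner may run control sessions, and record that person's role on the form. State as a limitation that expectation bias remains because women know their arm.

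The cost is protocol wording and one script, with no extra staff and no change in sample size. The downside is that some post-session scores may be missing with no chance to retake them; the completeness check is there to limit this.

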3.2. Control Group

This study has a control group. For the control group: a member of the research team, who may or not be a HT practitioner, will verify consent. Then they will ask the woman to complete baseline measurements of pain and anxiety. The subject will then be encouraged to have a quiet time session equivalent to the length of a Healing Touch session, with the lights dimmed. After the quite time, the team member will again measure the subject's levels of pain and anxiety.

3.3. Randomization

Randomization will be done through using a computerized randomization through the use of the following website: https://www.random.org/coins/ For Heads=intervention, For Tails=control.

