2.4. Number of Subjects

The total number of subjects expected to participate will be 160. Sample size estimates require a sample of 128 women, but to obtain an adequate sample size there will be an oversampling of up to 160 subjects, 40 at each study site.

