4. STATISTICAL CONSIDERATIONS/DATA ANALYSIS

4.1. Sample Size

Power analysis for an independent sample t-test was conducted in G-POWER to determine a sufficient sample size using an alpha of 0.05, a power of 0.80, a medium effect size (d = 0.5), and two tails. There will be an equal allocation of participants into each group. Based on the aforementioned assumptions, the desired sample size is 128 (64 in each group). The team will over sample in order to meet sufficient sample size. Planned recruitment will = 160 women (40 per study site).

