4.3. Data Storage

Information about study subjects will be kept confidential and managed according to the requirements of the Health Insurance Portability and Accountability Act of 1996 HIPAA. Privacy and confidentiality of all enrolled participants will be maintained through the use of a password protected data management spreadsheet. The spreadsheet will only be accessed on Inova computers, which are also password protected, by members of the study team who have undergone human subjects training. The spreadsheet will list all potential study subjects, including their name, medical record number and phone number, identified from the pre-surgical lists for the scheduled cesarean deliveries at each hospital site. Once a potential study subject has been screened over the phone for study eligibility and enrolled, they will receive a de-identified study "ID" which will consists of numbers and letters. The key linking the study ID to a patient's personal information will be maintained separately from collected data. Hard copies of the data collection forms will be kept in a locked metal storage file cabinet in the office of the Primary Investigator.

4.3.1.Data Management

Enrollment in the study consists of the following: A participant has signed and returned a consent form and HIPAA form in the electronic platform, AND a PI/SUB-I has confirmed consent via phone call or face to face conversation, AND the PI/SUB-I has signed the consent, AND the PI/SUB-I has screened the participant for continued eligibility AND assigned them to a study intervention. Women who complete a consent form but no other steps in the enrollment process will be reported on the spreadsheet as "healing touch provider not available", "inclusion criteria not met", "delivered before scheduled date".

Some participants may complete the consent process but cannot be scheduled for either Healing Touch or Quiet time due to availability of Healing Touch Providers. These participants will remain on the spreadsheet to maintain tracking of eligible participants, but will noted as "Healing Touch provider not available".

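### The web coin toss has no log or lock, and the plan's conflicting order of steps lets eligibility be judged after the arm is known; equal allocation holds only in expectation

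*Combined protocol and SAP*

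**What the plan says.** Section 3.3 is the whole account of randomization. It points to a coin-flipping page: "https://www.random.org/coins/ For Heads=intervention, For Tails=control". It does not say who tosses, when, whether tosses are made singly or in a batch, or what is recorded. It mentions neither blocks nor site strata. The reference list (Section 13) cites a different tool from the same website, a list randomizer.

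Section 4.3.1 defines enrollment as a chain of steps that ends with "AND the PI/SUB-I has screened the participant for continued eligibility AND assigned them to a study intervention". One role therefore does both, with eligibility named first. Women who complete a consent form but no later step are kept on a spreadsheet by reason: no Healing Touch (HT) provider, inclusion criteria failed, or early delivery. The arm is not among the items to be recorded for them.

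The abstract (Study Methodology), Section 3.1 and Section 3.5 give another order: a woman who completes the consent form is enrolled and randomized. Section 3.5 makes the conversation with the site investigator the second consent step, after the electronic form. Section 2.8, criterion 5, excludes women who deliver before their scheduled date.

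Section 4.1 states: "There will be an equal allocation of participants into each group". The target is given as "the desired sample size is 128 (64 in each group"), and "Planned recruitment will = 160 women (40 per study site").

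**The concern.** Randomization protects the comparison only if the arm cannot influence who enters and the first result stands. Here two things are left open.

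- **Repetition.** A toss on a public page can be made again. Without a required record, nobody could later show that the first result was used.
- **Eligibility judged after the toss.** If the toss follows the consent form, the consent conversation, the continued-eligibility check and the early-delivery exclusion can all come later, with the arm known.

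No bad faith is needed for the second route. Section 3.1 warns that a woman may miss HT because no provider is free or because she is discharged first, whereas Section 3.2 lets someone who is not an HT practitioner run the control session. If availability is settled only after the toss, losses can depend on the arm.

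Pain and anxiety are self-reported by women who know which session they had, and in the HT arm the practitioner who gives the session also obtains the baseline scores. The analysis in Section 4.2 is an unadjusted t-test with no stated rule that all randomized women are analysed as randomized. A difference introduced at entry would not be reliably separated from an effect of HT.

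A smaller matter is that independent tosses do not deliver fixed group sizes, overall or by site.

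**Working it through.** **1. The plan's own sample size.** Inputs from Section 4.1: "using an alpha of 0.05, a power of 0.80, a medium effect size (d = 0.5), and two tails", for an independent-samples t-test. With n per arm, the noncentrality is d / √(2/n) on 2n − 2 degrees of freedom.
- n = 63: power 79.5%.
- n = 64: noncentrality 0.5 / √(2/64) = 2.83, power 80.1%.

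The smallest n that reaches 80% is 64 per arm, so the total of 128 reproduces.

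**2. Order of steps, side by side.**

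| Source | When the arm is set | What can still follow |
|---|---|---|
| Abstract; 3.1; 3.5 | On completion of the consent form | Investigator's consent conversation, continued-eligibility check, early delivery (2.8) |
| 4.3.1 | After consent is confirmed and continued eligibility is screened | Nothing in the enrollment definition |

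The two cannot both be followed. Under the first row, a woman can be logged as ineligible or as lacking a provider after her arm is known. Under the second she cannot, on the face of it, but nothing prevents a repeated toss under either.

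**3. Size of a possible selection bias (assumed inputs).** The documents give no basis for a figure. Suppose 5% to 15% of women are affected and they differ by 0.5 SD:
- bias = 0.05 × 0.5 = 0.025 SD, up to 0.15 × 0.5 = 0.075 SD.

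With no true effect and 64 per arm, the noncentrality is bias / √(2/64), and the two-sided rejection rate at nominal 5% becomes:

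| Assumed shift (SD) | Noncentrality | Rejection rate |
|---|---|---|
| 0.025 | 0.14 | 5.2% |
| 0.075 | 0.42 | 7.1% |
| 0.1 | 0.57 | 8.7% |
| 0.2 | 1.13 | 20.2% |

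The last two rows lie beyond the assumed range and show only how fast the rate climbs.

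**4. Equal allocation under a fair toss.** The number in one arm is Binomial(N, 0.5).
- N = 128: P(exactly 64:64) = 7.0%; the central 95% range for one arm is 53 to 75.
- N = 160: P(both arms at least 64) = 99.1% before any loss.
- One site of 40: P(25:15 or worse) = 15.4%. At least one of four sites: 1 − (1 − 0.154)⁴ = 48.7%.

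Power for unequal arms uses noncentrality 0.5 / √(1/n₁ + 1/n₂):
- 64:64 gives 80.1%; 74:54 gives 79.2%; 75:53 gives 79.0%.
- Averaged over all splits of 128: 79.8%.
- At 160: 88.2% for 80:80, and 88.0% on average.

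**The case against.** The strongest reply is that Section 4.3.1, read alone, has the right order: eligibility, then assignment. Its reason codes apply to women who have done nothing beyond the consent form, and it says the provider problem can block either session, so those women may simply never have been assigned. That is a fair reading, and it removes the arm-driven exit wherever 4.3.1 is followed. It does not remove the conflict with the abstract and Sections 3.1 and 3.5, which govern the same step, and no rule says availability is settled before the toss.

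Much of the rest is inference from silence, and that limit stands. A reader might conclude that allocation is unconcealed and that one investigator both screens and tosses. The documents do not say so: a single fair toss cannot be predicted, Section 3.3 names no operator, and the role in 4.3.1 could be filled by two people. The cited list randomizer even leaves open that a list was intended. What the text supports is that no safeguard is described.

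A reader might also infer that unequal groups undermine the trial or confound site with treatment. They do not. Chance imbalance causes no systematic bias, the power cost is under one percentage point at 74:54, and Section 10 describes the four facilities as having the same resources and equipment. Finally, pre-session scores are taken, so a baseline difference in pain or anxiety would be visible and partly offset in a change score.

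**Conclusion.** The point holds in a limited form. As written, the plan permits repeated tosses without trace and, under the order in the abstract and Sections 3.1 and 3.5, exclusions made with the arm known and no arm recorded. Whether either would happen, and how much bias would follow, cannot be derived from the documents. The rise in the false-positive rate to about 5.2% to 7.1% rests wholly on the assumed 5% to 15% of women affected and the assumed 0.5 SD difference.

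Equal allocation is true in expectation and not guaranteed, overall or by site. To say that it fails, or that it costs meaningful power, would go beyond the figures.

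This should be fixed, because a missing allocation record cannot be rebuilt at analysis. The evidence does not show that the trial's result would be invalid.

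**What to change.** 1. Reconcile the abstract and Sections 3.1 and 3.5 with Section 4.3.1, so that one order of consent, eligibility and assignment applies throughout. Reconcile the list randomizer in the references with the coin toss in Section 3.3.
2. Replace the toss with a 1:1 list generated in advance in permuted blocks of varying size, stratified by the four sites, and held by an existing team member who neither screens nor schedules.
3. Release each assignment once, by sequentially numbered opaque envelopes, or through the electronic consent platform if it can do this. Release it only after eligibility is recorded as final and session availability is settled for either arm. Log date, time and study ID, and allow no second draw.
4. Track every randomized woman by arm, including those who later deliver early, withdraw or receive no session.

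The cost is a short amendment and a one-off list, with no extra participants. The downside is that an existing coordinator or data person must hold the list and keep it from those who screen. The documents do not say whether the consent platform can release assignments, so envelopes are the safer default.
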